4.2. Scientific Rationale for Study Design

The ibrutinib-rituximab combination in study PCYC-1127-CA resulted in a compelling and statistically significant efficacy profile over extended rituximab alone; the combination extended PFS and produced durable responses in both treatment naïve and previously treated participants. The rapid reduction in IgM levels, especially in patients at high-risk to develop hyperviscosity (>5 g/L),^{8,9,12} and the sustained improvement in hemoglobin levels, demonstrate the patient-related benefits of ibrutinib-based therapy in preventing hyperviscosity upon treatment initiation and improvement in cytopenias or symptoms, such as anemia and fatigue, typically the most common reasons for initiating treatment for WM. The clinical efficacy, improvement in disease-related symptoms, and long-term tolerability is reflected by the substantial prolongation of time-to-next treatment with ibrutinib-rituximab over rituximab alone.

Since no Japanese participants were enrolled in the global studies, the proposed study 54179060WAL2002 is designed based on PCYC-1127-CA study to confirm the efficacy of ORR and safety in Japanese patients with treatment naïve or relapsed/refractory WM. Primary endpoint will be ORR by IRC assessment instead of PFS because of very limited sample size and lack of a randomized control arm. Response assessment will be done based on the modified sixth IWWM (NCCN version 2, 2019)²⁷ response criteria same as in PCYC-1127-CA study.

Biomarker Collection

Blood samples for biomarker assessment will be collected at predose Week 1 to study pretreatment prognostic factors.

A somatic mutation of the MYD88 has been identified in nearly 90% of WM patients that appears to drive WM growth and proliferation.³⁵ Additionally, a group of somatic mutations in CXCR-4 (a chemokine receptor) gene that are similar to germline mutations in germline genetic WHIM syndrome (warts, hypogammaglobulinemia, infections, and myelokathexis¹⁰), have been found in around 30% of WM patients.^{1,2,15} The MYD88^{L265P} and CXCR4^{WHIM} somatic mutations statuses, which are important predictive biomarkers, will be evaluated in Japanese patients with WM for this study.

4.2.1. Study-Specific Ethical Design Considerations

Potential participants will be fully informed of the risks and requirements of the study and, during the study, participants will be given any new information that may affect their decision to continue participation. They will be told that their consent to participate in the study is voluntary and may be withdrawn at any time with no reason given and without penalty or loss of benefits to which they would otherwise be entitled. Only participants who are fully able to understand the risks, benefits, and potential AEs of the study, and provide their consent voluntarily will be enrolled.

This is an open-label, single arm study and all participants will receive the study intervention. Ibrutinib is considered as a novel treatment option specifically targeting signaling pathway involved in WM and has been approved for treatment of WM based on results of 2 pivotal studies in some countries including US and EU. It could be an additional treatment option for Japanese patients with WM. In this study, bone marrow biopsy and/or aspirate to be collected is considered to be a common practice and acceptable for participants participating in a cancer clinical study.

The total blood volume to be collected (see Section 8) is considered to be an acceptable amount of blood to be collected over this time period from the population in this study.

4.3. Justification for Dose

The proposed rituximab regimen of weekly dose for 4 weeks and 4 additional weekly infusions of rituximab reported higher response rates (44% and 48%)^{9,33} compared with standard dose (ie, 4 weekly infusions at 375 mg/m²) in WM.¹¹

The proposed dose for ibrutinib is 420 mg per day (3×140 mg capsules) administered once daily without interruption. In the Phase 2 study (PCYC-1118E), the 420 mg dose administered once daily appeared safe and favorable responses were seen in participants with previously treated WM. Combination of ibrutinib with rituximab was subsequently confirmed as safe and effective for WM in PCYC-1127-CA. In this study, PK of ibrutinib in Japanese patients will be evaluated and confirmed if it is consistent with non-Japanese patients. Given no drug-drug interaction is identified between ibrutinib and rituximab to date, and PK of ibrutinib has been confirmed as consistent between Japanese and non-Japanese patients, the proposed doses of both ibrutinib and rituximab in this study with Japanese WM patients are identical to those used in the global studies.

4.4. End of Study Definition

End of Study Definition

The end of study is considered as the last scheduled study assessment shown in the Schedule of Activities (SoA) (Section 1.3) for the last participant in the study. The final data from the study site will be sent to the sponsor (or designee) after completion of the final participant assessment at that study site, in the time frame specified in the Clinical Trial Agreement.

The study will be terminated before the defined end of study is reached if marketing approval is granted for the indication from the MHLW in Japan.

5. STUDY POPULATION

Screening for eligible participants will be performed within 30 days before administration of the study intervention. Refer to Section 5.4, Screen Failures for conditions under which the repeat of any screening procedures is allowed.

The Inclusion and Exclusion Criteria for enrolling participants in this study are described below. If there is a question about these criteria, the investigator must consult with the appropriate sponsor representative and resolve any issues before enrolling a participant in the study. Waivers are not allowed.

For a discussion of the statistical considerations of participant selection, refer to Section 9.2, Sample Size Determination.

5.1. Inclusion Criteria

Each potential participant must satisfy all of the following criteria to be enrolled in the study:

1. Japanese man or woman ≥ 20 years of age.
2. Clinicopathological diagnosis of WM in accordance with the consensus panel of the second IWWM.²³
3. Japanese patients with treatment naïve or relapsed/refractory WM:
 - a. Relapsed/refractory patients must meet following criteria:
 - 1) To have either documented disease progression or had no response (stable disease) to the most recent treatment regimen.
 - 2) In case of patients who have received treatment containing rituximab, those who have not been relapsed after the last rituximab-containing therapy <12 months since last dose of rituximab and have achieved at least a MR after the last rituximab-containing therapy should be included.
 - 3) To have received no more than 5 regimens. Separate lines of therapy are defined as single or combination therapies that are either separated by disease progression or by a >6 -month treatment-free interval.
4. Measurable disease defined as serum monoclonal IgM >0.5 g/dL.
5. Symptomatic disease meeting at least 1 of the recommendations from the second IWWM for requiring treatment.²⁸
 - a. Constitutional symptoms documented in the participant's chart with supportive objective measures, as appropriate, defined as one or more of the following disease-related symptoms or signs:
 - 1) Unintentional weight loss $\geq 10\%$ within the previous 6 months prior to screening

- 2) Fevers higher than 38.0°C for 2 or more weeks prior to screening without evidence of infection
- 3) Night sweats for more than 1 month prior to screening without evidence of infection
- b. Clinically relevant fatigue which is not relieved by rest due to WM
- c. Symptomatic hyperviscosity or serum viscosity levels >4.0 centipoises
- d. Lymphadenopathy which is either symptomatic or bulky (≥ 5 cm in maximum diameter)
- e. Symptomatic hepatomegaly or splenomegaly or organ tissue infiltration
- f. Peripheral neuropathy due to WM
- g. Symptomatic cryoglobulinemia
- h. Cold agglutinin anemia
- i. IgM related immune hemolytic anemia and/or thrombocytopenia
- j. Nephropathy related to WM
- k. Amyloidosis related to WM
- l. Hemoglobin ≤ 10 g/dL
- m. Platelet count $< 100,000$ cells/ μ L
- n. Serum monoclonal protein > 5 g/dL, with or without overt clinical symptoms

6. Eastern Cooperative Oncology Group (ECOG) performance status of ≤ 2 .

7. Adequate organ, hepatic and renal function defined as follows:

- a. Absolute neutrophil count (ANC) > 750 cells/ μ L independent of growth factor support within 7 days
- b. Platelets $> 50,000$ cells/ μ L independent of transfusion support within 7 days
- c. Hemoglobin ≥ 8.0 g/dL independent of transfusion support or growth factor support within 7 days
- d. Alanine aminotransferase (ALT) and aspartate aminotransferase (AST) $< 3.0 \times$ upper limit of normal (ULN)
- e. Total bilirubin $\leq 1.5 \times$ ULN (unless due to Gilbert's syndrome)
- f. Estimated creatinine clearance (CrCl) ≥ 30 mL/min (Cockcroft-Gault equation)

8. Prothrombin time /international normalized ratio (INR) $\leq 1.5 \times$ ULN and partial thromboplastin time (activated partial thromboplastin time [aPTT]) $\leq 1.5 \times$ ULN (unless abnormalities are unrelated to coagulopathy or bleeding disorder. When treated with warfarin or other vitamin K antagonists, then INR ≤ 3.0).

9. Woman of childbearing potential must have a negative, highly sensitive serum (β -human chorionic gonadotropin [β -hCG]) at screening and urine pregnancy test at Day 1 prior to the first dose of study intervention.
10. Criterion modified per Amendment 1
- 10.1 Women of childbearing potential must be practicing a highly effective, preferably user-independent method of birth control (failure rate of <1% per year when used consistently and correctly) during treatment with any drug in this study and for up to 12 months after the last dose of rituximab, 1 month after last dose of ibrutinib, consistent with local regulations regarding the use of birth control methods for participant participating in clinical studies. Women using hormonal contraceptives should add a barrier method.

Examples of highly effective methods of contraception are located in Section 10.5, Appendix 5, Contraceptive and Barrier Guidance and Collection of Pregnancy Information.

11. Criterion modified per Amendment 1
- 11.1 Women must agree not to donate eggs for the purpose of assisted reproduction during treatment and for 1 month after the last dose of ibrutinib and 12 months after last dose of rituximab.
12. During treatment, for a minimum of 1 spermatogenesis cycle (defined as 90 days) after receiving the last dose of ibrutinib, and for up to 12 months after last dose of rituximab, in addition to the user-independent highly effective method of contraception, a man:
 - a. who is sexually active with a woman of childbearing potential must agree to use a barrier method of contraception (eg, condom with spermicidal foam/gel/film/cream/suppository)
 - b. who is sexually active with a woman who is pregnant must use a condom
 - c. must agree not to donate sperm for the purpose of reproduction
13. Must sign an informed consent form (ICF) indicating that he or she understands the purpose of, and procedures required for, the study and is willing to participate in the study. Participants must be willing and able to adhere to the prohibitions and restrictions specified in this protocol.
14. Must be willing and able to adhere to the lifestyle restrictions specified in this protocol.

5.2. Exclusion Criteria

Any potential participant who meets any of the following criteria will be excluded from participating in the study:

1. Known histological involvement of the central nervous system by WM.
2. Rituximab treatment within the last 12 months before the first dose of study intervention.
3. Prior exposure to ibrutinib or other BTK inhibitors.
4. Received any WM-related therapy (eg, chemotherapy, immunotherapy, investigational intervention) ≤ 30 days prior to first administration of study intervention.
5. Plasmapheresis < 35 days prior to the initiation of study intervention, except when at least one screening serum IgM central assessment is performed > 35 days after the previous plasmapheresis and before the plasmapheresis during the screening period.
6. History of prior malignancy, except:
 - a. Malignancy treated with curative intent and with no known active disease present for ≥ 3 years before first dose
 - b. Adequately treated nonmelanoma skin cancer or lentigo maligna without evidence of disease
 - c. Adequately treated cervical carcinoma in situ without evidence of disease
 - d. Malignancy, which is considered cured with minimal risk of recurrence
7. Received live, attenuated vaccine within 4 weeks of first dose of study intervention.
8. Uncontrolled active systemic infection or infection requiring systemic treatment that was completed ≤ 14 days before the first dose of study intervention.
9. Currently active, clinically significant Child-Pugh Class B or C hepatic impairment according to the Child-Pugh classification (see Section 10.6, Appendix 6).
10. Inability or difficulty swallowing capsules, malabsorption syndrome, or any disease or medical condition significantly affecting gastrointestinal function.
11. Stroke or intracranial hemorrhage within 12 months prior to the first dose of study intervention.
12. Active, clinically significant cardiovascular disease, such as uncontrolled arrhythmia or Class 3 or 4 congestive heart failure as defined by the New York Heart Association Functional Classification; or a history of myocardial infarction, unstable angina, or acute coronary syndrome within 6 months prior to the first dose of study intervention.

13. Requires treatment with a strong CYP3A inhibitors (see Section [10.7](#), Appendix 7).
14. Positive test for human immunodeficiency virus (HIV) by history or at screening.
15. Active hepatitis C virus (HCV) or hepatitis B virus (HBV).
 - a. Active HBV: Participants who are positive for hepatitis B core antibody (HBcAb), hepatitis B surface antibody (HBsAb), hepatitis B surface antigen (HBsAg) must have a negative polymerase chain reaction (PCR) result before enrollment.
 - b. Active HCV: Participants who are positive for hepatitis C antibody must have a negative PCR result before enrollment and should have documented 24 weeks of sustained virologic response (SVR) in order to be eligible for the study.
16. Major surgery (eg, requiring general anesthesia), within 4 weeks of first dose of ibrutinib, or will not have fully recovered from surgery, or has surgery planned during the time the participant is expected to participate in the study.
17. Criterion modified per Amendment 1
- 17.1 Female participants who are pregnant, breastfeeding, or planning to become pregnant while enrolled in this study or up to 12 months after the last dose of rituximab or 1 month of last dose of ibrutinib.
18. Male participants who plan to father a child while enrolled in this study or within 3 months after the last dose of ibrutinib, and within 12 months after last dose of rituximab.
19. Any contraindication to ibrutinib or rituximab including hypersensitivity to the active substance or to any of the excipients of ibrutinib or rituximab per local prescribing information.
20. Received an investigational intervention (including investigational vaccines) or used an invasive investigational medical device within 4 weeks before the planned first dose of study intervention or is currently enrolled in an investigational study.
21. Any condition for which, in the opinion of the investigator, participation would not be in the best interest of the participant (eg, compromise the well-being) or that could prevent, limit, or confound the protocol-specified assessments.
22. Employee of the investigator or study site, with direct involvement in the proposed study or other studies under the direction of that investigator or study site, as well as family members of the employees or the investigator.

NOTE: Investigators should ensure that all study enrollment criteria have been met at screening. If a participant's clinical status changes (including any available laboratory results or receipt of additional medical records) after screening but before the first dose of study intervention is given such that he or she no longer meets all eligibility criteria, then the participant should be excluded from participation in the study. The required source documentation to support meeting the enrollment criteria are noted in Section 10.3 Appendix 3, Regulatory, Ethical, and Study Oversight Considerations.

5.3. Lifestyle Considerations

Potential participants must be willing and able to adhere to the following lifestyle restrictions during the course of the study to be eligible for participation:

1. Refer to Section 6.5, Concomitant Therapy for details regarding prohibited and restricted therapy during the study.
2. Agree to follow all requirements that must be met during the study as noted in the Inclusion and Exclusion Criteria (eg, contraceptive requirements).
3. The following guidance should be applied during the perioperative period for participants who require surgical intervention or an invasive procedure while receiving study intervention.
 - a. Minor Surgical Procedures
For minor procedures (such as a central line placement, needle biopsy, lumbar puncture [other than shunt reservoir access] thoracentesis, or paracentesis) study intervention should be held for at least 3 days prior to the procedure and should not be restarted for at least 3 days after the procedure. For bone marrow biopsies that are performed while the participant is on study intervention, it is not necessary to hold study intervention.
 - b. Major Surgical Procedures
For any surgery or invasive procedure requiring sutures or staples for closure, study intervention should be held at least 7 days prior to the intervention and should be held at least 7 days after the procedure and restarted at the discretion of the investigator when the surgical site is reasonably healed without serosanguineous drainage or the need for drainage tubes.
 - c. Emergency Procedures
For emergency procedures, study intervention should be held after the procedure for at least 7 days after the urgent surgical procedure.
4. Initial transient increases in serum IgM levels (IgM flare or tumor flare) are common (in up to 50% of patients) 3 to 4 weeks after initiation of rituximab therapy.^{9,12,33} This flare may persist for up to 4 months and does not indicate treatment failure but may

necessitate plasmapheresis to reduce hyperviscosity^{8,12,33} or other clinical symptoms (see Exclusion Criterion #5 for plasmapheresis conditions in the screening period).

- a. Plasmapheresis at the discretion of the treating physician should be considered in participants with IgM values above 5,000 mg/dL before start of the treatment regimen to avoid clinical symptomatic tumor flare upon administration of study intervention.
- b. Plasmapheresis should be considered in patients with signs of symptomatic hyperviscosity before start of the treatment regimen.
- c. Plasmapheresis should be considered in participants who developed a clinically symptomatic tumor flare (eg, hyperviscosity syndrome) upon administration of study intervention.
 - o This initial transient increase of IgM levels will most likely not indicate disease progression and participants may continue therapy with rituximab.
 - o Increase of IgM levels after the first 16 weeks of study treatment should be considered PD and further use of plasmapheresis should be discussed with the Medical Monitor.

In the event that a participant requires plasmapheresis prior to study treatment, the IgM level obtained prior to plasmapheresis should be considered as the baseline value and study intervention should be initiated shortly thereafter (not more than 7 days) after last plasmapheresis. IgM level obtained within 5 half-lives (ie, ≤ 35 days) after the last plasmapheresis should not be considered for response evaluation. An IgM level obtained more than 35 days after plasmapheresis can be used in response determination.

The IgM level prior to and after each plasmapheresis during the screening phase and during the study should be collected centrally.

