6. STUDY INTERVENTION

6.1. Study Intervention Administered

All eligible participants will be treated with study intervention and need to follow the dosing and toxicity management guideline described as follows. Study intervention administration must be captured in the source documents and the eCRF. Study-site personnel will instruct participants on how to store study intervention for at-home use as indicated in this protocol.

Study Intervention

Ibrutinib 420 mg (140 mg×3 capsules) orally administered daily beginning from Day 1 in Week 1 until disease progression or unacceptable toxicity.

Rituximab 375 mg/m² intravenous (IV) per prescribing information weekly for 4 consecutive weeks, followed by a second course of once-weekly rituximab for 4 consecutive weeks after a 12-week interval. Day 1 of Weeks 1 to 4 and Weeks 17 to 20 (total of 8 infusions of rituximab).

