8.4. Efficacy Assessments

Response assessments will be performed using the modified consensus criteria adapted from the sixth IWWM (NCCN version 2, 2019).²⁷

Progression of nodal and extranodal disease should be evaluated based on the revised criteria for malignant lymphoma described in the revised International Working Group for NHL.³ The spleen is considered nodal disease.

Efficacy evaluation will include the following components:

- Hematologic parameters by complete blood count (CBC)
- Quantitative serum IgS (IgA, IgG, and IgM)
- Quantitative serum-M protein (SPEP)
- Qualitative serum immunofixation, if applicable
- Radiographic evaluation, if applicable
- Bone marrow aspirate and biopsy, if applicable

If disease progression is suspected solely based on the results of a single examination or a single laboratory parameter (eg, IgM), this finding should be confirmed by a subsequent evaluation at least within 4 weeks from the first finding. Additional hematologic parameters, radiographic evaluation and bone marrow biopsy should be performed at the discretion of the treating physician to confirm PD if indicated. PD is defined as one of the following:

- A $\geq 25\%$ increase in serum IgM with a total increase of at least 500 mg/dL from nadir (Confirmation of the initial IgM increase is required when IgM is sole criterion for progressive disease.)

Note: Nadir for serum IgM is defined as the lowest serum IgM value obtained at any time from baseline onwards with the exception that serum IgM levels post-plasmapheresis will not be considered for up to 35 days.

- New symptomatic disease on the basis of malignant pleural effusion, Bing Neel (WM CNS disease) syndrome, amyloidosis or light chain deposition disease, or other paraprotein mediated disorder.
- New or recurrent involvement in the bone marrow

- Measurable nodal and extranodal disease will follow the definition of nodal progression by imaging in Section 8.4.6.1
- Appearance of new splenomegaly or $\geq 50\%$ increase from nadir in enlargement of the spleen
- Appearance of new extranodal disease

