8.5.1.1. Reporting of Tumor Flare

Therapy with rituximab in WM is commonly associated with a surge of IgM levels (IgM flare or tumor flare). This transient increase of IgM levels will most likely not indicate disease progression and participants may continue therapy with rituximab.

The Medical Dictionary for Regulatory Activities (MedDRA) does not support the reporting of "IgM flare" and therefore these events should be reported as an AE of 'tumor flare'. [Table 5](#) provides guidance on grading this particular event.

Table 5: Grading for Adverse Events of IgM Associated Tumor Flare

Tumor flare	
Grade 1	<25% IgM increase during rituximab therapy
Grade 2	≥25% IgM increase during rituximab therapy
Grade 3	IgM increase during rituximab therapy associated with clinical intervention (eg, plasmapheresis)
Grade 4	IgM increase during rituximab therapy associated with life-threatening consequences; urgent intervention indicated
Grade 5	Death

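### Section 5.3 calls any IgM rise after Week 16 progression, without the size threshold that Section 8.4 requires

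*Protocol*

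**What the plan says.** Section 5.3, item 4, deals with IgM flare and plasmapheresis. It says of the rise after starting rituximab: "This flare may persist for up to 4 months and does not indicate treatment failure". Item 4.c then states: "Plasmapheresis should be considered in participants who developed a clinically symptomatic tumor flare". Two sub-bullets follow. The first says that the initial transient rise most likely does not indicate progression. The second reads "Increase of IgM levels after the first 16 weeks of study treatment should be considered PD and further use of plasmapheresis should be discussed". The Medical Monitor is named as the person to consult.

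Section 8.4 holds the formal definition of progressive disease (PD). Its IgM limb is a rise of at least 25%, specified as an "increase in serum IgM with a total increase of at least 500 mg/dL from nadir". It adds: "Confirmation of the initial IgM increase is required when IgM is sole criterion for progressive disease". Nadir is the lowest value from baseline onwards, leaving out values for up to 35 days after plasmapheresis.

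Section 8.4 also makes the investigator responsible for disease status when deciding whether treatment continues. Sections 4.1, 7.1 and 8.2 require study intervention to stop at confirmed PD. ORR and PFS are assessed by the independent review committee (IRC).

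**The concern.** The protocol states two rules for when a late IgM rise is progression. Section 8.4 sets a relative size, an absolute size, a reference value and a confirmation step. The Section 5.3 bullet sets only a time, after the first 16 weeks, and assigns the label PD. It does not ask the investigator to evaluate for PD, and it does not refer to 8.4.

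The investigator acts on these rules, because the investigator's call decides whether treatment continues. A site that follows 5.3 as written could record progression, and eventually stop effective therapy, for a rise that another site applying 8.4 would not count.

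**Working it through.** **Inputs.** From Section 5.3, item 4.c: an increase after Week 16 is PD, with no minimum size. From Section 8.4: at least 25% and at least 500 mg/dL above nadir. The nadirs below are assumed, because the protocol gives none. No figure in the plan depends on this point, and the sample size of 14 is unaffected.

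**Step 1: the smallest rise that Section 8.4 counts.** Both limbs must be met, so the minimum rise is max(0.25 × nadir, 500 mg/dL). The limbs are equal at 500 / 0.25 = 2,000 mg/dL.

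| Assumed nadir (mg/dL) | 0.25 × nadir | Minimum rise in 8.4 | Value that must be reached |
|---|---|---|---|
| 1,000 | 250 | 500 | 1,500 |
| 1,500 | 375 | 500 | 2,000 |
| 2,000 | 500 | 500 | 2,500 |
| 3,000 | 750 | 750 | 3,750 |
| 4,000 | 1,000 | 1,000 | 5,000 |

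Every rise above zero and below the third column is PD by the literal 5.3 wording and not PD by the IgM limb of 8.4.

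**Step 2: example rises after Week 16.**

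| Rise (mg/dL) | Change | 5.3, literal | 8.4 |
|---|---|---|---|
| 1,000 to 1,200 | +200; 200/1,000 = 20% | PD | Not PD: below 500 and below 25% |
| 1,500 to 1,950 | +450; 450/1,500 = 30% | PD | Not PD: below 500 |
| 3,000 to 3,600 | +600; 600/3,000 = 20% | PD | Not PD: below 750 |
| 4,000 to 4,900 | +900; 900/4,000 = 22.5% | PD | Not PD: below 1,000 |
| 3,000 to 3,900 | +900; 900/3,000 = 30% | PD | Size met; confirmation needed |

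**Step 3: does confirmation reconcile the rules?** Section 8.4 asks for a repeat evaluation within about 4 weeks whenever progression is suspected on one laboratory parameter, and it makes no exception for late rises. This protects against a single stray value. It does not settle the size. If 1,200 mg/dL is found again on repeat testing, the increase is confirmed, yet it is still +200 against a required +500. The 5.3 wording still says PD and 8.4 still says not.

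**Step 4: where the disagreement has effect.** It reaches the investigator's progression call and, through confirmed PD, the decision to stop treatment. It does not directly enter the IRC-assessed ORR or PFS.

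**The case against.** PD is a defined term in Section 8.4. The 5.3 bullet uses the term inside plasmapheresis advice and does not claim to redefine it. It follows a sub-bullet on the initial transient rise and a statement that flare may last up to 4 months, so the natural reading is that after 16 weeks a rise is no longer excused as flare. The only action it asks for is a discussion about plasmapheresis. Discontinuation is tied to confirmed PD, and Section 8.4 says treatment should in general continue until confirmation. Item 4.c also concerns symptomatic cases, and the lower nadirs in the examples are not shown to be such cases.

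Most of this stands. It is why the intent is probably harmless and the consequence small. It does not make the wording correct: the bullet classifies a rise where it should call for an evaluation, and confirmation leaves the size conflict in place (step 3). The gap also widens at higher IgM, so it is not confined to low values.

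A reader might also infer a firm conflict with Section 8.5.1.1 and Table 5. That section says "This transient increase of IgM levels will most likely not indicate disease progression and participants may continue therapy with rituximab", and Table 5 grades rises during rituximab therapy as flare. Four of the 8 infusions fall in Weeks 17 to 20, after the 16-week cut (day 112; Week 17 Day 1 is 7 × 16 + 1 = day 113). The documents do not support that stronger claim:

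- Table 5 names no weeks and gives guidance on grading an event reported as flare.
- Sections 5.3 and 6.1.2.5 speak of the initial rise, and footnote l of the Schedule of Activities ties the flare IgM samples to starting treatment.
- Section 6.1.2.5 provides for further tests to separate flare from progression.
- The protocol does not say whether flare recurs with the second course.

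At most, the Table 5 wording could be read to include Weeks 17 to 20.

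**Conclusion.** The Section 5.3 bullet is wrong as written: read literally, it states a progression rule that contradicts Section 8.4. The disagreement covers rises up to just under 500 mg/dL for nadirs up to 2,000, 750 at 3,000 and 1,000 at 4,000. The thresholds come from the protocol; the nadirs are assumed. The conflict depends on the literal reading, and the bullet probably means only that late rises lose the presumption of flare.

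The point is minor. A reader might infer that ORR or PFS is biased, or that participants will be taken off treatment at any small rise. The text supports neither. Both endpoints are read by the IRC, so any effect on them is indirect, through early stopping. Stopping itself requires confirmed PD. The number of participants affected cannot be derived from the protocol, and none is claimed.

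**What to change.** Replace the Section 5.3 bullet with wording such as: *After the first 16 weeks, a rise in IgM is no longer presumed to be flare. Evaluate it for PD by the Section 8.4 criteria, including confirmation, and discuss any further plasmapheresis with the Medical Monitor.* This keeps the probable intent and leaves one definition of PD.

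The cost is one bullet in a protocol amendment, with no new data, visits or analyses. If the sponsor wants to settle whether Table 5 covers the second rituximab course, that clarification belongs in Section 8.5.1.1; a change to 5.3 would not achieve it.
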